Blood – PK blood sample/s M8891		X	X	X	X	X						Table 4 PK samples will be collected only until Day 1 Cycle 2

Activity / Assessment	Screening	On Treatment Visits								EOT ^a	Safety F/U ^b	Notes
	M8891	M8891 + Cabozantinib										
		Cycle 1		Cycle 2-4		Cycle 5	Cycle 7 and on					After Cycle 7, visits on Day 1 of every third cycle
Cycle Day	-28 to -2	-1 (-24h) ^c	1	8	15	1	15	1	1 of every third cycle	Within 7 days of last intervention	30 days after last dose	For rescreening see Section 5.1.1 CCI
Visit Window			±1	±1	±2	±2	±3	±3	+7	+7		
Blood – PK blood sample/s cabozantinib			X	X	X	X						Table 4 PK samples will be collected only until Day 1 Cycle 2
CCI												
CCI												
Blood – ctDNA ^j			X	X	X		X	X	X			
Tumor assessment (RECIST v1.1)	X ^k	X ^k			X ^l		X ^l	X ^l	X			
Drug administration												
	Dispensing every Day 1 of each cycle until Cycle 5 and then on Cycle 7 and afterwards every third cycle											
M8891 Administration		X	M8891 given in clinic on C1D1 and taken once daily at home thereafter until study treatment is discontinued									Section 5.1.3.2
Cabozantinib Administration			Cabozantinib given in clinic on C1D1 and taken once daily at home thereafter until study treatment is discontinued									Section 5.1.3.2

AE: Adverse event; ctDNA: circulating tumor DNA; CT: Computed tomography; ECG: Electrocardiogram; ECOG PS: Eastern Cooperative Oncology Group Performance status; EOT: End of treatment; MRI: Magnetic resonance imaging; mRCC: Metastatic renal cell carcinoma; PK: Pharmacokinetic; RECIST: Response Evaluation Criteria in Solid Tumors; SAE: Serious adverse event.

a. Subjects who discontinue treatment will undergo EOT visit procedures.

b. Safety follow up will be performed if SAE is not recovered at the EOT.

CCI

c. For Contraception and postmenopausal status see [Appendix 1](#).

d. Physical exam, hematology, biochemistry, and coagulation do not have to be repeated on Day -1, Cycle 1 (predose) if performed within 48 hours as a screening/baseline assessment.

e. Free T4 and TSH must be performed at screening, until Cycle 7 on Day 1 of each odd cycle (C1, 3, 5, 7), after Cycle 7 on Day 1 of every third cycle (7, 10, 13, etc), and at EOT (if not performed within the last 8 weeks). Thyroid Function test may be performed more frequently if clinically indicated.

f. Serology should be done only at screening and do not have to be repeated on Day -1, Cycle 1 if performed within 28 days as a screening/baseline assessment.

CCI

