- Imaging analysis must be using the same technique during the study, e.g. it's not allowed to use CT scan at baseline then change to MRI during the study. Tumor response will be assessed, within 1 week prior to Day 1 of Cycles 3, 5, and 7, and every third cycle thereafter. Subjects who discontinue treatment will undergo EOT visit procedures.

Table 4

Schedule of Pharmacokinetic, Electrocardiogram Assessments and Food Guidance during Part 2A M8891 Combined with Cabozantinib, mRCC, Dose Escalation

Treatment Day	Time h (\pm min) ^{a,b}	ECG ^c	PK M8891	PK Cabozantinib
Day -1, C1	Pre-dose (-60 min)	X	X ^d	
	1 (\pm 5)		X ^d	
	2 (\pm 10)	X	X ^d	
	3 (\pm 15)		X ^d	
	4 (\pm 15)		X ^d	
	6 (\pm 15)	X	X ^d	
	8 (\pm 15)		X ^d	
D1 C1	Pre-dose (-60 min)	X	X	X
	1 (\pm 5)		X	
	2 (\pm 10)	X	X	X
	3 (\pm 15)		X	
	4 (\pm 15)		X	
	6 (\pm 15)	X	X	X
D8 C1	Pre-dose (-60 min)	X	X	X
	2 (\pm 5)	X	X	X
D15 C1	Pre-dose (-60 min)	X	X	X
	1 (\pm 5)		X	
	2 (\pm 10)	X	X	X
	3 (\pm 15)		X	
	4 (\pm 15)		X	
	6 (\pm 15)	X	X	X
D1C2	Pre-dose (-60 min)	X	X	X
	2 (\pm 10)	X	X	X
D1C3-5	Pre-dose (-60 min)	X		
	1 (\pm 5)	X		
D1C7 (and Day 1 of every third cycle)	Pre-dose (-60 min)	X		
	1 (\pm 5)	X		

C: Cycle; D: Day; ECG: Electrocardiogram; eCRF: Electronic case report form; mRCC: Metastatic renal cell carcinoma; PK: Pharmacokinetics.

a. At visits where assessment time points (ECG and PK) coincide with each other

- 1) Perform vital signs assessments at first
- 2) ECG assessments slightly before the specific collection time point
- 3) PK assessments at scheduled collection time point.

b. Actual collection times should be documented in the eCRF.

- c. Standard triplicate (within 2 min) 12-lead ECG will be obtained after the subject has been rested in semi-recumbent position for at least 5 min at the indicated times. ECGs will be also performed during the End of Treatment and Safety Follow-up Visit (30 ± 7 days). Triplicate ECGs will be read locally. The calculated QTcF interval average of the three 12-lead ECGs must be ≤ 450 ms for males and ≤ 470 ms for females for eligibility. Subjects, in which the calculated QTcF interval average increases to > 500 ms or > 60 ms change over baseline during treatment, must interrupt study treatment until further clinical evaluations (See Section 7.4.5).

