4.1.2 Secondary Objectives

Secondary objectives are:

- To evaluate the safety profile and tolerability of M8891 as a single agent
- To investigate the PK profile of M8891 as single agent
- To assess the antitumor activity of M8891 as single agent according to Response Evaluation Criteria in Solid Tumors (RECIST) v1.1
- To determine the recommend Phase II dose (RP2D) as single agent.

CCI

4.2

Part 2, M8891 combined with Cabozantinib, mRCC

In Part 2 of this study, M8891 combined with cabozantinib will be administered in subjects with mRCC.

4.2.1

Part 2A, Dose Escalation

Table 6

Part 2A Objectives and Endpoints

Objectives	Endpoints (Outcome Measures)

Primary
 
To determine the recommended dose for expansion (RDE) (MTD, if reached) of M8891 combined with cabozantinib in subjects with mRCC, based on safety, tolerability, and antitumor activity	
Occurrence of DLTs in subjects with mRCC receiving M8891 combined with cabozantinib during the first 22-day treatment cycle (21 days of M8891 combined with cabozantinib, preceded by 1 day of M8891 alone) based on predefined set of AEs.Occurrence of TEAEs (including TEAEs leading to death or discontinuation of treatment) in subjects with mRCC receiving M8891 combined with cabozantinib. Any AEs that occur or worsen between start of study intervention and 30 days after end of study intervention will be considered TEAEs.Study clinically relevant abnormal changes in clinical laboratory measures from baseline, vital signs, ECOG performance status, and ECGs from start of study intervention to 30 days after end of study interventionObjective response according to RECIST v1.1 as assessed by Investigators

Objectives	Endpoints (Outcome Measures)

Secondary
 
• To characterize the PK profile of M8891 (single and multiple dose exposure) combined with cabozantinib in subjects with mRCC• To further assess antitumor activity of M8891 combined with cabozantinib in subjects with mRCC	
• PK parameters of M8891 in terms of C_{max}, t_{max}, AUC_{0-t} on Day 1 Cycle 1, (combined with cabozantinib, single dose)• PK parameters of M8891 in terms of C_{max}, t_{max}, AUC_{0-t} on Day 8 and Day 15 Cycle 1, and Day 1 Cycle 2 (combined with cabozantinib, multiple dose)
CC1	

[figure not shown]

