4.2.2 Part 2B, Expansion Cohort

Table 7 **Part 2B Objectives and Endpoints**

Objectives	Endpoints (Outcome Measures)
Primary	
• To determine recommended Phase II dose (RP2D) of M8891 combined with cabozantinib in subjects with mRCC based on antitumor activity and safety• Occurrence of study serious AEs including deaths from first dose of study intervention to 30 days after end of study intervention• Study clinically relevant abnormal changes in clinical laboratory measures from baseline, vital signs, ECOG PS, and ECGs from start of study intervention to 30 days after end of study intervention• Occurrence of TEAEs (including deaths) from start of the study intervention to 30 days after end of the study intervention• Objective response, according to RECIST v1.1 as assessed by Investigators
Secondary	
• To assess other measures of antitumor activity of M8891 combined with cabozantinib in subjects with mRCC• DoR according to RECIST v 1.1 criteria as assessed by Investigators• PFS time according to RECIST 1.1 criteria as assessed by Investigators 
• To characterize the PK profile of M8891 (single and multiple dose exposure) in subjects with mRCC• Plasma concentrations of M8891 on Day 1, Day 8 and Day 15 Cycle 1, (combined with cabozantinib, multiple dose)

CC1

AE: Adverse event; DoR: Duration of response; DLT Dose limiting toxicity; ECG: Electrocardiogram; ECOG PS: Eastern Cooperative Oncology Group Performance Status; CCI [REDACTED]; mRCC: Metastatic renal cell carcinoma; MTD: Maximum tolerated dose; PFS: Progression-free survival; PK: Pharmacokinetic; RECIST: Response Evaluation Criteria in Solid Tumors; RP2D: Recommended Phase II dose; TEAE-Treatment emergent adverse event; CCI [REDACTED]; CCI [REDACTED]

5 **Investigational Plan**

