Each part of the study will include a Screening period of up to 28 days, a study intervention period consisting of 21-day cycles of M8891 single agent (Part 1) and M8891 combined with cabozantinib (Part 2), an End of Study Intervention visit (within 7 days), and a Safety Follow-up period of 30 (\pm 7) days. Subjects who discontinue study intervention for any reason will complete the End of Study Intervention and Safety Follow-up visits. In Part 2A, before Cycle 1 of all dose levels, subjects will receive a single dose of M8891 in the morning in fed conditions (Day -1, Cycle 1) and the PK profile of M8891 will be evaluated pre-dose, 1, 2, 3, 4, 6, 8 and 24h (Day 1, Cycle 1) after administration (Section 5.1.3.2.1). Subsequently on Day 1 Cycle 1, subjects will initiate

treatment with M8891 combined with cabozantinib QD orally every morning under fasted conditions.

Study duration per subject is approximately 8 months for Part 1, and 12 months for Part 2 including screening, treatment and follow up.

[figure not shown]
The design of this study is presented in

Figure 1 and a detailed Schedule of Assessments (SoAs) is provided in Table 1, Table 2, Table 3, Table 4, and Table 5.

Figure 1

Study Design

AE: Adverse event; DL: Dose level; FBE Free-base equivalent; MTD: Maximum tolerated dose; QD: Once daily; SMC: Safety Monitoring Committee; RP2D: Recommended Phase 2 Dose; mRCC: metastatic renal cell carcinoma; **CCI** [REDACTED].

- a. The MTD of M8891 single agent will be defined, and RP2D of M8891 single agent suggested, by the SMC.
- b. Subjects should have progressed to 1 or more previous lines of systemic anticancer therapy, excluding treatment with cabozantinib.
- c. Cabozantinib will be given at the approved 60 mg FBE daily dosage with dosage adjustments to 40 mg or 20 mg permitted to manage AEs.

CCI [REDACTED]

CCI [REDACTED]

- f. 30 subjects evaluable for response.
- g. The DLT assessment period for Part 2A is the Cycle 1 (= 22 days, 21 days of M8891 combined with cabozantinib, preceded by 1 day of M8891 alone) of study treatment. The rest of the Cycles in Part 2A are 21-day cycles of M8891 combined with cabozantinib.
- h. See Section 8.5.1 for the Bayesian two-parameter logistic regression model.

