For Part 1, all subjects will complete an End of Treatment (EOT) Visit 30 (\pm 3) days after the last dose of study drug. For Part 2, all subjects will complete an EOT visit within 7 days after the last dose of study drug. For both Part 1 and Part 2, subjects with serious AEs (SAEs) ongoing at EOT Visit must be followed during the safety follow-up by the Investigator until stabilization or until the outcome is known, unless the subject is documented as “lost to follow-up”.

Subjects who tolerate M8891 (or M8891 combined with cabozantinib) without significant clinically relevant toxicities may continue to receive trial treatment, at the Investigator’s discretion or after consultation with the Sponsor’s physician, as long as there is no evidence of disease progression.

5.2

Discussion of Trial Design

This is a 2-part, Phase I/Ib, first in human, multicenter, open-label trial of M8891 single agent in solid tumors and M8891 combined with cabozantinib in mRCC, administered daily.

5.2.1

Dose Selection

5.2.1.1

Part 1, M8891 Single Agent, Solid Tumors

ICH guideline S9 has been considered as the reference guideline for the determination of the first-in-human starting dose, i.e., a dose that is expected to have pharmacologic effects and reasonably safe to use.

Based on the toxicity profile of M8891 administered to rats and dogs in the 2 pivotal 4-week repeat-dose oral toxicity studies, defining NOAELs of 3 mg/kg in rats and 0.75 mg/kg in dogs, the dog was identified to be the most sensitive species (Table 11). The NOAEL of 0.75 mg/kg dose in dogs also corresponded to the highest non-severely toxic dose (HNSTD). According to ICH guideline S9, when the non-rodent is the most appropriate species, 1/6 of the HNSTD is considered an appropriate starting dose. Hence, the proposed first-in-human starting dose for Part 1 of the

study was calculated to be 7.5 mg (rounded to 7 mg)/subject/day. In the first cohorts of subjects with late stage advanced malignancies, this dose will be given as a once daily oral administration.

Table 11 **First in Human Starting Dose Calculated from Results of 4-week Repeat-Dose Toxicity Studies in Rats and Dogs**

Species	Treatment regimen	NOAEL (mg/kg/day)	Safety factor	Starting dose based on NOAEL (mg per subject) ^a
Rat	Daily, oral	3	1/10	18
Dog	Daily, oral	0.75 ^b	1/6	7.5

NOAEL: No observed adverse effect level.

^a Based on the assumption of 60 kg patient.

^b Corresponds to the highest non-severely toxic dose.

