5.7 Definition of End of Trial

A clinical trial protocol may not be considered closed as long as:

- Any subject is still receiving any IMP
- Visits specified by the protocol are still taking place
- Procedures or interventions according to the protocol are still being undertaken in any subject
- The post-treatment follow-up period, defined in the clinical trial protocol as being part of the trial, has not yet been completed for any subject.

If the trial is not prematurely discontinued for a reason given in Section 5.6, the end of the trial is defined as the last subject enrolled in the trial having treatment up to 2 years or either stopped M8891 (or M8891 combined with cabozantinib), i.e., having withdrawn because of disease progression, death, unacceptable toxicity, or Investigator/subject decision, or having completed the EOT visit and Safety Follow-up visit if applicable. Subjects who are on ongoing treatment at this time may be offered continued treatment outside of the study under observation of local regulations.

[figure not shown]
6 Investigational Medicinal Product and Other Drugs Used in the Trial

The term “Investigational Medicinal Product” (IMP) refers to an active substance or a placebo being tested or used as a reference therapy in a clinical trial, including products that have a marketing authorization but are formulated, packaged, or administered differently from the authorized form, used for an unauthorized indication, or used to gain further information about the authorized form. The IMP for this study is M8891.

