7.4.1.3 Definition of the Adverse Event Reporting Period

The AE reporting period for safety surveillance begins when the subject is initially included in the trial (date of first signature of first informed consent) and continues until the EOT visit and through the safety follow-up period for SAEs. Subjects with SAEs ongoing at EOT Visit must be followed during the safety follow-up.

Any SAE assessed as related to M8891 must be reported whenever it occurs, irrespective of the time elapsed since the last administration of M8891.

7.4.1.4 Procedure for Reporting Serious Adverse Events, Adverse Events of Special Interest and Dose Limiting Toxicities

Serious Adverse Events

In the event of any new SAE occurring during the reporting period, the Investigator must immediately (within a maximum of 24 HOURS after becoming aware of the event) inform the Sponsor or its designee in writing. All written reports should be transmitted using the SAE Report Form, which must be completed by the Investigator following specific completion instructions.

In exceptional circumstances, an SAE (or follow-up information) may be reported by telephone; in these cases, a written report must be sent immediately thereafter by fax or e-mail. Names, addresses, and telephone and fax numbers for SAE reporting will be included in the trial-specific SAE Report Form.

Relevant pages from the eCRF may be provided in parallel (for example, medical history, concomitant drugs). Additional documents may be provided by the Investigator, if available (for example, laboratory results, hospital report, autopsy report). In all cases, the information provided on the SAE Report Form must be consistent with the data about the event recorded in the eCRF.

The Investigator must respond to any request for follow-up information (for example, additional information, outcome, final evaluation, other records where needed) or to any question the Sponsor/designee may have on the AE within the same timelines as those noted above for initial reports. This is necessary to ensure prompt assessment of the event by the Sponsor or designee and (as applicable) to allow the Sponsor to meet strict regulatory timelines associated with expedited safety reporting obligations.

Requests for follow-up will usually be made via the responsible Monitor, although in exceptional circumstances the Global Drug Safety department may contact the Investigator directly to obtain further information or to discuss the event.

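### Part 2 safety endpoints run to 30 days after treatment, but the protocol's rules on AE reporting and the 30-day visit do not collect them that far, and they contradict each other

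*Protocol*

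**What the plan says.** **Endpoints.** For Part 2A, Table 6 (Section 4.2.1) states: "Any AEs that occur or worsen between start of study intervention and 30 days after end of study intervention will be considered TEAEs". For Part 2B, Table 7 (Section 4.2.2) lists "Occurrence of TEAEs (including deaths) from start of the study intervention to 30 days after end of the study intervention". Both tables give the same 30-day limit for clinically relevant changes in laboratory values, vital signs, ECOG PS and ECGs. All of these are primary endpoints.

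**AE reporting period.** Under Section 7.4.1.3, reporting begins at informed consent "and continues until the EOT visit and through the safety follow-up period for SAEs". Section 7.4.1.6 takes the final AE outcome at EOT and follows only ongoing SAEs beyond it. SAEs related to M8891 are reportable without a time limit.

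**EOT timing.** Section 5.1.4: "For Part 2, all subjects will complete an EOT visit within 7 days after the last dose of study drug". In Part 1 the EOT visit is instead 30 (±3) days after the last dose.

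**Who attends the 30-day visit.** The Safety F/U footnotes of Tables 2 and 3 say: "Safety follow up will be performed if SAE is not recovered at the EOT". Section 5.7 speaks of a subject "having completed the EOT visit and Safety Follow-up visit if applicable". Section 5.1 says the opposite: "Subjects who discontinue study intervention for any reason will complete the End of Study Intervention and Safety Follow-up visits", with follow-up at 30 (±7) days.

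**What is done there.** In Tables 2 and 3 the Safety F/U column marks only AE assessment. Footnote c of Tables 4 and 5 adds that "ECGs will be also performed during the End of Treatment and Safety Follow-up Visit", and Appendix III adds laboratory tests at Safety Follow-up.

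**The concern.** An endpoint defined over 30 post-treatment days needs data collected over those days in every subject. For Part 2, one set of passages supports that and another does not. A site that works from the schedule footnotes and Section 7.4.1.3 stops recording new non-serious AEs at EOT and brings back only subjects with an open SAE. A site that works from Section 5.1 brings back everyone who discontinues.

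Two consequences follow. First, the observation window for the same primary endpoint differs between sites. Second, under the footnotes it depends on outcome, because subjects with an unrecovered SAE are watched longer than the rest. A subject without an open SAE also has no scheduled contact at which a new late SAE would be found, although such an SAE remains reportable if the site learns of it.

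The recommended dose for expansion (Part 2A) and the recommended Phase II dose (Part 2B) both rest partly on safety. Section 8.5.3 tabulates safety by dose level, so uneven windows would carry into those tables.

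**Working it through.** The plan states no figure to reproduce. The check sets the passages side by side and then counts days.

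**1. Passages compared (Part 2)**

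| Item | Supports collection to day 30 | Stops short of day 30 |
|---|---|---|
| TEAEs | Tables 6 and 7; AE row marked at Safety F/U in Tables 2 and 3 | Section 7.4.1.3 (SAEs only after EOT); Section 7.4.1.6 (final outcome at EOT) |
| 30-day visit | Section 5.1 (all who discontinue) | Table 2 and 3 footnotes (open SAE only); Section 5.7 (conditional) |
| Laboratory tests | Tables 6 and 7; Appendix III | Not marked at Safety F/U in Tables 2 and 3 |
| ECG | Tables 6 and 7; footnote c of Tables 4 and 5 | Not marked at Safety F/U in Tables 2 and 3 |
| Vital signs, ECOG PS | Tables 6 and 7 | Not marked at Safety F/U; no passage places them after EOT |

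The column reading was checked by counting cells. The AE row has 11 marks in 11 columns in Table 2 and 10 in 10 in Table 3. No other row reaches the Safety F/U column. The vital-sign, ECG and ECOG PS rows have complete cell counts with that cell empty.

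**2. Post-treatment days without collection of new non-serious AEs**

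This assumes Section 7.4.1.3 and the footnotes are followed. Gap = 30 − day of EOT.

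- EOT on day 7: 30 − 7 = 23 days; 23/30 = 76.7%.
- EOT on day 0: 30 − 0 = 30 days; 30/30 = 100%.
- EOT on day 14, if the +7 window in Tables 2 and 3 is added to the 7 days (7 + 7 = 14): 30 − 14 = 16 days; 16/30 = 53.3%.

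**3. The same gap as a share of the whole TEAE window**

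- Subject on study for the planned 12 months. Assumption: 365 − 28 (screening) − 30 (follow-up) = 307 treatment days, so the window is 307 + 30 = 337 days. Shares: 16/337 = 4.7%, 23/337 = 6.8%, 30/337 = 8.9%.
- Part 2A subject who stops at the end of the 22-day Cycle 1. Window: 22 + 30 = 52 days. Shares: 16/52 = 30.8%, 23/52 = 44.2%, 30/52 = 57.7%.

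**4. If Section 5.1 is followed instead**

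The ±7 window allows a visit on day 23. Then 30 − 23 = 7 days, or 7/30 = 23.3%, lie after the last contact.

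**5. Subjects affected**

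Planned numbers are 6–15 in Part 2A and 30–40 in Part 2B: between 6 + 30 = 36 and 15 + 40 = 55.

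**6. Does the SAP settle it?**

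No. SAP Section 6 limits that plan to the monotherapy dose escalation. Its TEAE definition (Section 15.2) also ends 30 days after the last dose, so it depends on the same collection.

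**The case against.** The strongest reply is that most of the protocol supports the 30-day window. Section 5.1, footnote c of Tables 4 and 5 and Appendix III all treat the 30-day visit as planned. The AE row is marked there without restriction to SAEs, and Section 7.4.1.2 has subjects asked about changes in their condition at each visit. The outliers may be carried over from Part 1, where the same footnote does little harm because EOT is itself at about day 30. That explanation is plausible, but it does not tell a site which text to follow. Even if Section 5.1 prevailed, Section 7.4.1.3 would still limit reporting after EOT to SAEs.

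A second reply is that little depends on the gap. SAEs are covered, and all deaths after the first dose are tabulated (Section 8.5.3). The Part 2A model uses Cycle 1 DLTs, unacceptable toxicity in Part 2B is judged on treatment (Section 5.1.3.2.2), futility is based on response, and all analyses are descriptive. This stands, and it limits the severity. It does not change the fact that a primary endpoint would not be collected as defined.

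A third reply concerns the evidence and the size. Days are not events, and the documents give no rate of late AEs; that is accepted. Adding +7 to the 7 days may count one allowance twice, so the day-14 case is only a lower bound for the gap. One of the two page headers of Table 2 shows +7 rather than ±7 for follow-up, and on that reading the day-23 gap disappears for Part 2A. A few table rows (tumor assessment, urine pregnancy test) look shifted in the extracted text, but the rows relied on here do not.

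**Conclusion.** The concern holds and should be fixed. For Part 2 the protocol gives incompatible instructions on safety data between EOT and day 30, and one set of them fails to collect the primary TEAE endpoint as defined. With EOT on day 7, that set leaves 23 of 30 post-treatment days (77%; range 53% to 100%) without collection of new non-serious AEs. Against the whole TEAE window the loss is about 7% (5–9%) for a 12-month subject, assuming 307 treatment days, and 44% (31–58%) for a Part 2A subject who stops at the end of Cycle 1. Up to 55 subjects fall under these rules.

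The damage is confined to the Part 2 TEAE and safety-change endpoints as reported. The missing data are new non-serious AEs and the day-30 laboratory, ECG, vital-sign and ECOG PS findings, together with a scheduled contact for subjects who have no open SAE. DLT and response endpoints are not affected. Part 1 does not have this gap, because its EOT visit is at about day 30.

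**What to change.** Reconcile Sections 5.1, 5.7, 7.4.1.3 and 7.4.1.6, Tables 2 to 5 and Appendix III with the endpoint windows in Tables 6 and 7. For Part 2:

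- Remove the unrecovered-SAE condition from the Safety F/U footnotes of Tables 2 and 3, and align Section 5.7.
- Amend Section 7.4.1.3 so that all AEs, serious or not, are collected in every subject through 30 days after the last dose, and bring Section 7.4.1.6 into line.
- Set the contact on or after day 30, for example with a window of 0 to +7 days, and say whether it is a clinic visit or another form of contact.
- For laboratory tests, ECG, vital signs and ECOG PS, choose one of two courses. Either mark them in the Safety F/U column of Tables 2 and 3, or end those endpoint windows at EOT and align Appendix III and footnote c of Tables 4 and 5.

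Shortening the TEAE window itself to EOT would be the poorer choice. It would depart from the 30-day TEAE definition in SAP Section 15.2 and from the roughly 30-day collection in Part 1.

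The cost is protocol wording, slightly more AE data entry, and one contact per Part 2 subject that Section 5.1 already promises. That contact must be a clinic visit if the laboratory, ECG, vital-sign and ECOG PS windows stay at day 30.
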